10.11. Appendix 11: Protocol Amendment History

The Protocol Amendment Summary of Changes Table for the current amendment is located directly before the Table of Contents (TOC).

**VERSION HISTORY****Table 1: SAP Version History Summary**

SAP Version	Approval Date	Change	Rationale
1		Not Applicable	Initial release

## 1. INTRODUCTION

The statistical analysis plan (SAP) for the 73763989PAHPB2007 phase 2 describes the statistical analyses, and definitions to assess the efficacy, safety, tolerability, and PK of the combination of JNJ-73763989 (JNJ-3989), nucleos(t)ide analogs (NAs), and pegylated interferon-alpha2a (PegIFN- $\alpha$ 2a) in long-term ( $\geq 2$  years of NA treatment) virologically suppressed, HBeAg-negative, chronic HBV-infected (CHB), adult participants.

This study is part of the platform trial PLATFORMMPAHPB2001 in participants with CHB. The protocol for 73763989PAHPB2007 constitutes the Intervention Specific Appendix that describes all the specific and/or additional features of this study complementing the common design elements of the platform trial described in the Master Protocol.

This SAP is to be interpreted in conjunction with the clinical protocol amendment 1 finalized on 6 October 2021, and with the Master Protocol Amendment-3 for PLATFORMPAHPB2001 finalized on 21 January 2021.

Details on pharmacokinetic (PK) and pharmacokinetic/pharmacodynamic (PK/PD) analyses will be described in a separate analysis and modelling plan.

### 1.1. Objectives and Endpoints

Objectives	Endpoints
Primary	

 
To evaluate the efficacy in terms of HBsAg changes from baseline for the treatment regimens of 24 weeks of JNJ-3989 + 24 weeks of NA + 12 or 24 weeks of PegIFN-<math>\alpha</math>2a (with immediate or delayed start of PegIFN-<math>\alpha</math>2a treatment), as compared to NA standard of care treatment.
 
	
 
Proportion of participants with a reduction of at least 2 log10 in HBsAg levels from baseline at Week 24 (EOSI).
 

Secondary	

 
To evaluate the safety and tolerability of the study intervention.
 
	
 
Safety and tolerability including but not limited to the proportion of participants with (S)AEs and abnormalities in clinical laboratory tests (including hematology, blood biochemistry, blood coagulation, urinalysis, urine chemistry, renal biomarkers), 12-lead ECGs, vital signs, and ophthalmologic and physical examinations throughout the study.
 

 
To evaluate the efficacy of the study intervention at the end of the 24-week treatment period.
 
	
 
Proportion of participants meeting the protocol-defined NA treatment completion criteria at Week 24 (EOSI) or FU Week 2 results.
 

 
To evaluate the efficacy of the study intervention during the FU period in those participants who meet the protocol-defined NA treatment completion criteria based on the Week 24 or FU Week 2 results.
 
	
 
Proportion of participants with HBsAg seroclearance at FU Week 24 and 48 (ie, 24 and 48 weeks after completion of all study interventions at Week 24) without re-starting NA treatment.
 

Objectives	Endpoints
	
 
Proportion of participants with HBV DNA <LLOQ at FU Week 24 and 48 (ie, 24 and 48 weeks after completion of all study interventions at Week 24) without re-starting NA treatment.
 
Frequency of virologic and/or biochemical flares.
 
Proportion of participants requiring NA re-treatment.
 


 
To evaluate the efficacy of the study intervention as measured by blood markers (such as HBsAg, HBeAg, HBV DNA, and ALT) during the study intervention and follow-up (FU) period.
 
	
 
Proportion of participants with HBsAg, HBeAg, HBV DNA, and ALT levels below/above different cut-offs over time.
 
Proportion of participants with HBsAg seroconversion.
 
Change from baseline over time in HBsAg.
 
Time to achieve HBsAg seroclearance/seroconversion, and/or HBV DNA <LLOQ.
 

 
To evaluate the frequency of virologic breakthrough throughout the study.
 
	
 
Proportion of participants with virologic breakthrougha.
 

 
To evaluate the PK of JNJ-3989 (JNJ-3924 and JNJ-3976), and optionally of NA and PegIFN-<math>\alpha</math>2a.
 
	
 
PK parameters of JNJ-3989 (JNJ-3924 and JNJ-3976).
 
Optionally, PK parameters of NA and/or PegIFN-<math>\alpha</math>2a.
 

Exploratory	

 
To explore host and viral baseline and on-treatment markers associated with end of study intervention and/or off-treatment response.
 
	
 
Association of baseline characteristics and baseline/on-treatment viral and host blood markers with selected on or off-treatment efficacy variables.
 

 
To explore changes in the severity of liver disease.
 
	
 
Changes in fibrosis (according to Fibroscan liver stiffness measurements) at EOSI and the end of the FU period versus baseline.
 

 
To explore efficacy of the study intervention in terms of changes in HBV RNA and hepatitis B core-related antigen (HBcrAg) levels during the study intervention and FU period.
 
	
 
Changes from baseline in HBV RNA and HBcrAg levels over time.
 

 
To explore the relationship of PK with selected pharmacodynamic (PD) parameters of efficacy and safety.
 
	
 
Relationship of various PK parameters with selected efficacy and safety endpoints.
 


 
To explore the HBV genome sequence during the study intervention and FU period.
 
	
 
Assessment of intervention-associated mutations over time.
 

 
To explore HBV-specific T-cell responses during the study intervention and FU period.b
 
	
 
Changes from baseline in HBV-specific peripheral blood T-cell responses over time.b
 

Objectives	Endpoints

 
To explore the efficacy of NA re-treatment in participants who meet the criteria for NA re-treatment.
 
	
 
Proportion of participants who reach HBV DNA <LLOQ after re-start of NA treatment during the FU period.
 

 
To explore medical resource utilization (MRU) to manage participants during study intervention and follow-up.
 
	
 
Number and duration of medical care encounters, including surgeries, and other selected procedures (inpatient and outpatient)
 
Duration of hospitalization (total days length of stay, including duration by wards; e.g. intensive care unit)
 
Number and character of diagnostic and therapeutic tests and procedures
 
Outpatient medical encounters and treatments (including physician or emergency room visits, tests and procedures, and medications)
 

a For the definition of virologic breakthrough, refer to 5.4.1.1.13.

b Peripheral blood mononuclear cell (PBMC) samples for immune analyses will be collected at selected sites only.

## 1.2. Study Design

This is a Phase 2, open-label, 3-arm, multicenter study to assess efficacy, safety, tolerability, and pharmacokinetics of treatment with JNJ-3989, NA, and PegIFN- $\alpha$ 2a in long-term ( $\geq 2$  years of NA treatment) virologically suppressed, HBeAg-negative, chronic HBV-infected, adult participants.

Approximately 102 long-term ( $\geq 2$  years of NA treatment) virologically suppressed, HBeAg-negative, chronic HBV-infected, adult participants,  $\geq 18$  (or the legal age of consent in the jurisdiction in which the study is taking place) to 65 years of age (inclusive) will be enrolled in this study.

[figure not shown]
This open-label study will be conducted in 3 periods:

- Screening Period (4 weeks [if necessary, e.g. for operational reasons, can be extended to a maximum of 8 weeks decided on a case-by-case basis and in agreement with the Sponsor]).
- Treatment Period (24 weeks):
  - Arm 1 (N=34): JNJ-3989 for 24 weeks + NA for 24 weeks + PegIFN- $\alpha$ 2a for 24 weeks.
  - Arm 2 (N=34): JNJ-3989 for 24 weeks + NA for 24 weeks + PegIFN- $\alpha$ 2a from Week 12 till Week 24.
  - Arm 3 (N=34): JNJ-3989 for 24 weeks + NA for 24 weeks + PegIFN- $\alpha$ 2a from baseline till Week 12.
- Follow-up (FU) Period (48 weeks), starting at Week 24.

The total duration of individual participation will be up to 72 weeks (screening not included). Participants will be considered to have completed the study if they have completed all the assessments of the end of study (EOS) visit (ie, FU Week 48).

A schematic overview of the trial is presented in [Figure 1](#).

**Figure 1: Schematic Overview of the Study**

ALT: alanine aminotransferase; DNA: deoxyribonucleic acid; EOS: end of study; EOSI: end of study intervention; FU: follow-up; HBeAg: hepatitis B e antigen; HBV: hepatitis B virus; JNJ-3989: JNJ-73763989; N: number of participants; NA: nucleos(t)ide analog; PegIFN-α2a: pegylated interferon alpha-2a; Q4W: every 4 weeks; QD: once daily; QW: once weekly; Rand: randomization.

a If all of the NA treatment completion criteria (see Clinical Protocol Section 6.5.1, NA Treatment Completion, for more details) are met based on the Week 24 results, NA will be stopped at the next scheduled visit (ie, FU Week 2), otherwise NA treatment will continue during the complete FU period.

*Note:* Participants who are close to meeting the protocol-defined NA treatment completion criteria with the Week 24 results, and do meet the criteria based on the FU Week 2 results may be allowed to stop NA at FU Week 4, after consultation with the Sponsor.

Participants who meet the protocol-defined NA treatment completion criteria will be monitored closely during the 48-week FU Period with a study visit at least once every 4 weeks. NA treatment should be re-started in accordance with the NA re-treatment criteria are met (see Clinical Protocol Section 6.5.2, NA Re-treatment Criteria During Follow-up, for more details).

At baseline, participants who meet the eligibility criteria will be randomized in a 1:1:1 ratio to Arm 1, Arm 2, or Arm 3. Randomization will be stratified by absolute HBsAg level (<1,000 IU/mL versus ≥1,000 IU/mL) at baseline and country grouping as proxy for HBV genotype (GT) at enrollment, with 3 levels: Poland (predominantly GT-A) versus Russia (predominantly GT-D) versus all other countries (other or mixed GT prevalence). Participants in Arm 2 who no longer meet the PegIFN-α2a eligibility criteria (see Exclusion Criterion A24 in Clinical Protocol Section 5.2, Exclusion Criteria) at Week 12, based on available laboratory or clinical data, will continue JNJ-3989 and NA treatment until Week 24 without PegIFN-α2a.

All participants will receive the last dose of JNJ-3989 at Week 24 and the last dose of PegIFN-α2a at Week 23 (Arms 1 and 2) or Week 11 (Arm 3). They will start the FU period after the Week 24 visit. If the protocol-defined NA treatment completion criteria (Section 5.4.1.1.1) are met based on the Week 24 results, treatment with NA will be stopped at the next scheduled visit (ie, FU

Week 2), otherwise NA treatment will continue during the complete FU period. Note: Participants who are close to meeting the protocol-defined NA treatment completion criteria with the Week 24 results, and do meet the criteria at FU Week 2 results may be allowed to stop NA at FU Week 4, upon prior discussion with the Sponsor.

The NA treatment completion criteria which take ALT, HBV DNA, HBeAg, and HBsAg levels into consideration, have been selected to ensure that only participants with a higher chance of achieving sustained off-treatment response are allowed to stop all study intervention. Participants who meet the protocol-defined NA treatment completion criteria will be monitored closely during the 48-week FU Period and participants should re-start NA treatment if NA re-treatment criteria are met (see Clinical Protocol Section 6.5.2, NA Re-treatment Criteria During Follow-up, for more details).

If a participant prematurely discontinues JNJ-3989 (ie, before Week 24), the participant will have an early WD visit and will enter the 48-week follow-up period as per the Schedule of Activities, unless the participant withdraws consent.

If a participant prematurely discontinues PegIFN- $\alpha$ 2a (ie, before Week 23 [Arms 1 and 2] or before Week 11 [Arm 3]), treatment with JNJ-3989 and NA should be continued as planned.

If a participant withdraws prematurely from the study, the reason for withdrawal (if known) should be documented in the case report form (CRF) and in the source document. Participants who withdraw consent will be offered an optional safety follow-up visit to occur on the day of consent withdrawal.

An internal Data Review Committee (DRC) will be commissioned for monitoring safety of participants enrolled in this study. In addition, an Independent Flare Expert Panel (IFLEP) will be appointed.

## **2. STATISTICAL HYPOTHESES**

The primary hypothesis of this study is that at least one of the combination regimens of JNJ-3989+NA+PegIFN- $\alpha$ 2a is more efficacious than NA treatment alone (standard of care), as measured by the primary efficacy endpoint, the proportion of participants who achieved a reduction of at least 2  $\log_{10}$  in HBsAg levels from baseline at Week 24. Because the study does not include a control arm, the hypothesis is formulated assuming a fixed external NA control response rate of 2% in terms of the primary efficacy endpoint.

## **3. SAMPLE SIZE DETERMINATION**

A sample size of 30 participants per arm yields >95% statistical power to detect a  $\geq 30\%$  difference in at least one arm in the proportions of participants with a reduction of at least 2  $\log_{10}$  in HBsAg levels from baseline at Week 24 versus a fixed proportion of  $\leq 2\%$ , assumed for external control (NA treatment). Statistical power to test the primary hypothesis was assessed for each of the intervention arms, separately, using an exact test for a single proportion with a one-sided Type 1 error rate of 0.05 and applying the Hochberg procedure for multiple comparisons adjustment. The

assumed external control value is based on the data of the NA control arm in virologically suppressed HBeAg negative participants in study 73763989HPB2001 (REEF-1).

The total study sample size is 102 participants (34 per arm) with 1:1:1 randomization ratio to one of the three intervention arms, assuming an approximate 10% attrition rate.

For the secondary set of pairwise comparisons of the primary efficacy endpoint among the 3 study intervention arms (Arm 1 versus Arm 2, Arm 1 versus Arm 3, and Arm 2 versus Arm 3) and using a 2-sample binomial test, the planned sample size yields about 68% power to detect a significant difference of at least 30%. This is assuming the lowest response rate at Week 24 to be 50% in one of the intervention arms, and 80% in one or both of the other 2 arms and applying the Hochberg procedure to control the 1-sided Type 1 error rate at 0.05 level. The assumption of 50% response rate was derived from the analysis of 73763989HPB2001 (REEF-1) on-treatment data.

#### 4. POPULATIONS (ANALYSIS SETS) FOR ANALYSIS

Due to a potential impact of future Coronavirus Disease (COVID-19) pandemics on the study data collection, study treatment adherence and study conduct, the modified Full Analysis Set (mFAS) and modified IFN-FAS (mIFN-FAS) are defined to target the estimation of effects without the pandemic-related influences.

The primary set for efficacy analyses will be the FAS, and for the safety analyses the safety set. The IFN-FAS and modified FAS/IFN-FAS analysis sets will be used if there is a relevant difference from the FAS (>5% of participants in total).

**Table 2: Analysis Sets for Analysis**

Analysis Sets	Description
Screened	All participants who signed the ICF for the Master Protocol and the ICF specific for this ISA.
Enrolled	All participants who were enrolled in this ISA.
Randomized	The randomized analysis set includes all participants who were randomized in the study.
Full Analysis Set (FAS)	All participants who were randomly assigned to an intervention arm in this ISA and received at least 1 dose of study intervention within this ISA. Participants will be analyzed according to the study intervention they were randomly assigned to.
Modified FAS	All participants who were randomly assigned to an intervention arm in this ISA and received at least 1 dose of study intervention within this ISA excluding those participants who, because of COVID-19 or similar pandemics related reasons, withdrew prematurely from the study prior to Week 24 (EOSI), or had no efficacy assessment for the primary endpoint. COVID-19 or similar pandemics related reasons may include for example missed visits due to travel restriction, shortage of lab kits at the planned visit, missed collection of blood sample at key time points for the primary efficacy endpoint etc. Participants will be analyzed according to the study intervention they were randomly assigned to.

Analysis Sets	Description
IFN-FAS	All participants who were randomly assigned to an intervention arm in this ISA and received at least 1 dose of PegIFN- $\alpha$ 2a within this ISA. Participants will be analyzed according to the study intervention they were randomly assigned to.
Modified IFN-FAS	All participants who were randomly assigned to an intervention arm in this ISA and received at least 1 dose of PegIFN- $\alpha$ 2a within this ISA excluding those participants who, because of COVID-19 or similar pandemics related reasons, withdrew prematurely from the study prior to Week 24 (EOSI), or had no efficacy assessment for the primary endpoint. COVID-19 or similar pandemics related reasons may include for example missed visits due to travel restriction, shortage of lab kits at the planned visit, missed collection of blood sample at key time points for the primary efficacy endpoint etc. Participants will be analyzed according to the study intervention they were randomly assigned to.
Safety	All participants who received at least 1 dose of study intervention within this ISA. Participants will be analyzed according to the study intervention they actually received.
Per Protocol Analysis Set (PP)	All participants in the FAS who do not have any of the selected major protocol deviations that may affect the assessment of efficacy in terms of the primary endpoint at Week 24. The selected major protocol deviations for efficacy analysis purposes that will be used to identify the participants included in the PP set are described in Section 6.4. Participants will be analyzed according to the study intervention they were randomly assigned to.
Pharmacokinetics Analysis Set	All participants who received at least 1 dose of study intervention and have at least 1 valid blood sample drawn for PK analysis.

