10.10. Appendix 10: Study Conduct During a Natural Disaster

GUIDANCE ON STUDY CONDUCT DURING THE COVID-19 PANDEMIC

It is recognized that the Coronavirus Disease 2019 (COVID-19) pandemic may have an impact on the conduct of this clinical study due to, for example, self-isolation/quarantine by participants and study site personnel; travel restrictions/limited access to public places, including hospitals; study site personnel being reassigned to critical tasks.

The sponsor is providing options for study related participant management in the event of disruption to the conduct of the study. This guidance does not supersede any local or government requirements or the clinical judgement of the investigator to protect the health and well-being of participants and site staff. If, at any time, a participant's travel to the study site is considered to be dangerous, study participation may be interrupted, and study follow-up conducted. If it becomes necessary to discontinue participation in the study, the procedures outlined in the protocol for discontinuing study intervention will be followed.

If, as a result of the COVID-19 pandemic, scheduled visits cannot be conducted in person at the study site, they will be performed to the extent possible remotely/virtually or delayed until such time that on-site visits can be resumed. At each contact, participants will be interviewed to collect safety data. Key efficacy endpoint assessments should be performed if required and as feasible. Participants will also be questioned regarding general health status to fulfill any physical examination requirement.

Every effort should be made to adhere to protocol-specified assessments for participants on study intervention, including follow up. Modifications to protocol-required assessments may be permitted via COVID-19 Appendix after consultation with the participant, investigator, and the Sponsor. Missed assessments/visits will be captured in the clinical trial management system for protocol deviations. Discontinuations of study interventions and withdrawal from the study should be documented with the prefix "COVID-19-related" in the CRF.

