- For participants unable to visit the study site, direct-to-patient (DTP) shipment or handover to a caregiver or delegate of oral study intervention, as well as PegIFN- α 2a, may be implemented, where allowed per local regulations^a and if requested by the treating study physician. Where DTP shipments or handover to delegates are deemed necessary, the process must be coordinated between the site and Sponsor staff following standard DTP procedures for arranging shipment and adhering to associated approvals and documentation requirements.
- JNJ-3989 should always be administered by a nurse at the study site or, if site visits are not possible, at the participant's home. Refer to Section 6.4, Study Intervention Compliance, in case a scheduled administration of study intervention (JNJ-3989, NA, or PegIFN- α 2a) is missed.

Continuation of Study Intervention:

- Any issue with continuation and/or provision of study intervention should be discussed with the Sponsor and should be well documented.
- Study intervention should be continued if, in the assessment of the investigator, it does not result in risk to the participant. If at any time the participant's safety is considered at risk due to study intervention, study intervention will be temporarily or permanently discontinued,

^a Delivering PegIFN- α 2a is not applicable for sites in countries that do not allow PegIFN- α 2a self-injection.

while every effort should be made to maintain follow-up on study. The benefit of continuing study intervention should be assessed by the investigator for each individual participant, considering the potential impact of reduced direct clinical supervision on participant safety.

- If a participant develops a SARS-CoV-2 infection, the investigator should contact the Sponsor to discuss plans for study intervention and follow-up. A decision to continue study intervention should be made by the investigator depending on symptoms and concomitant medication(s) used for the treatment of COVID-19. Study intervention must be discontinued if prohibited medication is used.
- When a participant, for whom study intervention has been interrupted, recovers from suspected or confirmed SARS-CoV-2 infection or related disease and all adverse events (AEs) related to SARS-CoV-2 infection improve to Grade ≤ 1 , the investigator should discuss with the Sponsor about resuming study intervention.

COVID-19 vaccination during the study:

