**D) Intercurrent events:**

- Treatment discontinuation prior to Week 24: if the participant discontinued treatment prior to Week 24 then s/he will be considered non-responder (composite strategy).
- Major protocol deviations affecting efficacy: Table 13 identifies the deviations considered intercurrent event. Participants with such deviations and who have missing data for the endpoint will be considered as non-responders (composite strategy). For all other deviations not considered intercurrent events, the data are used regardless of the occurrence of major protocol deviations (treatment policy strategy).
- Deaths prior to Week 24 are handled in a composite strategy as participants who die prior to Week 24 will be considered as non-responders.

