### **5.3.2.1.2. Data Included**

The main analysis of the primary endpoint will be conducted using the FAS. The IFN-FAS and modified FAS/IFN-FAS analysis sets will be used if there is a relevant difference from the FAS ( $>5\%$  of participants in total).

Week 24 response status data from the selected population analysis set, after taking into account all the intercurrent events and applying the intercurrent event strategies in Section 5.3.2, will be included.

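### The pandemic-adjusted analysis sets do not clearly exclude participants who stop treatment for a COVID-19-related reason but stay in the study, and the estimand scores those participants as non-responders

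*SAP*

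**What the plan says.** SAP section 4 justifies the modified sets by a possible pandemic effect on three areas, one of them adherence: "study data collection, study treatment adherence and study conduct, the modified Full Analysis Set (mFAS" and its IFN counterpart "are defined to target the estimation of effects without the pandemic-related influences". The FAS remains the primary efficacy set. The modified sets are used only if they differ from the FAS by more than 5% of all participants.

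In SAP Table 2 both modified sets carry the same exclusion. It covers participants who, for COVID-19 or similar pandemic reasons, "withdrew prematurely from the study prior to Week 24 (EOSI), or had no efficacy assessment for the primary endpoint". The examples given, which are open-ended, are missed visits, shortage of lab kits and missed blood samples.

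For the main estimand, SAP 5.3.2 part D says "if the participant discontinued treatment prior to Week 24 then s/he will be considered non-responder (composite strategy"). It makes no exception for cause. SAP 5.3.2.1.2 carries the rule into whichever set is being analysed: Week 24 response data from that set, "after taking into account all the intercurrent events and applying the intercurrent event strategies in Section 5.3.2, will be included".

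Protocol Appendix 10 treats stopping treatment and leaving the study as separate events: "Discontinuations of study interventions and withdrawal from the study should be documented with the prefix" COVID-19-related. It also requires treatment to be discontinued when prohibited medication is used, in the paragraph on participants who develop SARS-CoV-2 infection. Protocol 4.1 sends participants who stop JNJ-3989 early to a withdrawal visit and then into the 48-week follow-up.

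**The concern.** The exclusion rule covers data collection and study withdrawal but does not mention the adherence effect that section 4 names. A participant who needs a prohibited medicine for COVID-19, stops study treatment and remains in follow-up has suffered a pandemic-related loss of adherence. Neither limb of the exclusion plainly reaches that person, and the composite rule turns the stop into a failure inside the set meant to show the effect without such losses.

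Two things are at stake. The supportive response rates could be pulled down by the influence they are supposed to remove, and the between-arm contrasts distorted if stops are uneven across the PegIFN schedules. If these participants do not count as exclusions, the modified analysis may also not be triggered when it should be.

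**Working it through.** **1. Does the text exclude such a participant?**

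- *Withdrawal limb:* not met, because the participant is still in the study.
- *No-assessment limb:* unclear. SAP Table 3 ends the treatment period at early discontinuation, and follow-up begins the next day. SAP 5.1.3 assigns visits within phase, and in Table 4 the Week 24 window (days 156 to 183) exists only in the treatment phase.
  - Stop and withdrawal visit on day 85: follow-up day 1 is study day 86. A sample on study day 169 is follow-up day 169 − 86 + 1 = 84, which falls in the Follow-up Week 12 window (72 to 99). There is then no Week 24 value, and one could argue the limb applies. It is equally arguable that it does not, because HBsAg was sampled and only the labelling removed it.
  - Stop and withdrawal visit on day 160: the sample falls in the Week 24 window. An assessment exists, so the participant is retained, and is failed for stopping before Week 24.
- *PegIFN stopped alone:* Protocol 4.1 keeps JNJ-3989 and NA going, so a Week 24 sample is expected. SAP 5.1 defines study treatment as all three agents, and 5.3.2 does not say whether stopping any one of them or all of them counts.

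**2. Does another planned analysis deal with them?** The supplementary per-protocol estimand (SAP 5.3.3) uses the same non-responder rule. Sensitivity estimators 2 and 3 apply the 5.3.2 intercurrent-event strategies first. Table 13 can remove participants for disallowed medication (rows 33–38) or missed doses (rows 40–42), but only case by case, and it does not list COVID-19-related discontinuation.

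**3. The plan's own figures (SAP section 3), reproduced as a base.**

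- Attrition: 30/(1 − 0.10) = 33.3, rounded up to 34 per arm, 102 in total.
- Exact test against 2%, n = 30, strictest Hochberg step 0.05/3: reject at 4 or more responders. Power at 32% is 99.5%, consistent with the stated >95%.
- Pairwise 80% versus 50%, n = 34, one-sided 0.05/3, power = Φ{[Δ − z√(2p̄(1−p̄)/n)] / √[(p₁(1−p₁) + p₂(1−p₂))/n]}. With Δ = 0.30, p̄ = 0.65 and z = 2.128 this gives 68.8%, against the stated 68% or so.

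**4. Illustration.** The documents give no expected number of COVID-19 treatment stops, so k per arm is assumed, with stopping unrelated to outcome. The rate with stoppers kept as failures is p(34 − k)/34. With stoppers excluded it is p.

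| True rate | k = 2, kept | k = 4, kept | Excluded |
|---|---|---|---|
| 80% | 75.3% | 70.6% | 80% |
| 50% | 47.1% | 44.1% | 50% |
| 32% | 30.1% | 28.2% | 32% |

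The 30-point contrast becomes 75.3 − 47.1 = 28.2 points (k = 2 in both arms) or 70.6 − 44.1 = 26.5 points (k = 4 in both). If stops occur only in the 80% arm it becomes 25.3 or 20.6 points.

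Pairwise power from the formula above, treating the diluted rates as binomial:

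- k = 2 in both arms: 60.7% kept, 65.9% excluded.
- k = 4 in both arms: 53.3% kept, 62.7% excluded.
- Stops only in the 80% arm, kept: 51.2% (k = 2), 34.4% (k = 4).

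Test against 2% at a true 32%, n = 34, reject at 4 or more responders: power is P[Bin(34 − k, 0.32) ≥ 4] = 99.8% at k = 0 and 99.5% at k = 4.

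**5. Trigger.** 0.05 × 102 = 5.1, so at least 6 participants are needed. Two stops per arm is 6/102 = 5.9%. Whether that reaches the trigger depends on the reading in step 1.

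**The case against.** The strongest reply is that Table 2 may already remove many of these people. After an early JNJ-3989 stop, later samples belong to follow-up visits, so often no Week 24 value exists, and the listed pandemic reasons are open-ended. This stands in part. A reader might infer that every such stopper has a Week 24 sample and that nobody is excluded, but Tables 3 and 4 do not support that. What remains is that membership of the set turns on a windowing argument the SAP never makes, and can differ with the day of stopping.

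Second, a reader might infer that everyone who drops PegIFN alone becomes an automatic failure. That holds only if stopping any single agent counts as discontinuing treatment, which the SAP does not say.

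Third, the Appendix 10 instruction that treatment may stop "while every effort should be made to maintain follow-up on study" might be taken as describing a pandemic stop. Its sentence concerns a participant judged at risk from the study intervention. Prohibited medication used for COVID-19 is the clearer route, and much of Appendix 10 is aimed at keeping participants on treatment.

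Fourth, the Table 13 exclusions offer partial cover, but only by case review, as shown above. Finally, excluding people for a post-randomization event brings selection, particularly if stops are tied to tolerability and differ by PegIFN schedule. That is fair. It is the same kind of selection the modified sets already accept for withdrawals, and a separate intercurrent-event strategy would be an alternative.

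**Conclusion.** The point holds as a mismatch between the stated purpose of the modified sets and their definition. COVID-19-related treatment discontinuation with continued follow-up is not clearly excluded, is scored as failure, and may not count toward the trigger.

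Its reach is limited. The modified sets are supportive and conditional, and their definition does not enter the FAS analysis. A reader might infer that the primary conclusion is at risk, but the test against 2% has power of at least 99.5% with up to 4 forced failures in an arm. The effect is on supportive response rates (about 5 to 9 points at a true 80% with 2 to 4 stops of 34) and on between-arm comparisons. Those sizes rest on an assumed number of stops and on stopping being unrelated to outcome. Under that second assumption exclusion restores the true rate; otherwise it need not. The change is worth making because it is cheap, but it is not a flaw in the primary analysis.

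**What to change.** In the Modified FAS and Modified IFN-FAS rows of SAP Table 2, add a third ground for exclusion, for COVID-19 or similar pandemic reasons: *or discontinued study treatment prior to Week 24*. Identify these participants by the COVID-19-related prefix in the CRF. State that discontinued treatment has the same any-agent or all-agents meaning here as in SAP 5.3.2, and say there which one it is. Count these participants toward the >5% trigger.

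Settle the wording before outcome data are examined, since a later change to set membership in an open-label study would look data-driven.

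The cost is one clause in two rows plus a definition, with no new data and no change to the primary analysis. The supportive set becomes slightly smaller and takes on some further post-randomization selection.
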